7.4 Analysis Plan

All outcomes will be binary (e.g. tested – yes/no) and will be analyzed using a modified Poisson regression model^{27,28} with log link to estimate risk ratios (RRs) and identity link to estimate risk differences (RDs) in order to provide both relative and absolute measures of intervention effect. Such an approach assumes a Poisson distribution for the binary outcome and then 'fixes' the estimated standard errors to correct for model misspecification. We minimize clustering of outcomes by outlet with highly controlled intervention delivery and careful outcome measurements by research assistants. However, to account for possible clustering due to multiple individuals being randomized within different (randomly-sampled) outlets we will use a generalized estimating equations (GEE) approach with exchangeable working covariance matrix, Kauerman-Carroll correction and robust standard errors (to correct for model misspecification due to specifying a Poisson distribution)^{29,30}. The outcome will be regressed on

2 binary indicators, one each for the higher subsidy level of the two subsidies (50% RDT subsidy and 100% ACT subsidy), together with their interaction and a vector of potential confounder variables (e.g., age, gender) to account for possible imbalances between study arms. Although we hypothesize that there will be no evidence of a (statistical) interaction (see Sample Size details above), we will test for this interaction and, if significant, will separately report the effects of each subsidy conditional on levels of the other subsidy. In the absence of an interaction, we will estimate the overall ACT subsidy effect and the overall RDT subsidy effect by taking relative contrasts from the model. All analyses will be based on the intention-to-treat principle whereby all clients will be included in the analysis irrespective of whether they complied with the intervention.

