## **1.2 Study Hypotheses**

### **1.2.1 Primary Hypotheses**

RDT uptake (i.e. the proportion of clients who are tested with an RDT) will increase when the price of the RDT is reduced from \$0.40 (0% subsidy) to \$0.20 (a 50% subsidy), averaged over the ACT price levels.

RDT uptake will increase when the price of the ACT conditional on a positive test is reduced from \$0.40 to \$0 (67% subsidy vs 100% subsidy), averaged over the RDT price levels.

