### **2.4 Sample Size Justification**

Our sample size calculations are based on the expected changes in testing uptake with each of the price changes for the two commodities (RDT and ACT). We expect that reducing the price of the RDT from \$0.40 USD to \$0.20 will increase the percentage of clients who choose to get tested by 15 percentage points. We also expect that reducing the ACT price, conditional on a positive test result, from \$0.40 to \$0.00 will increase the uptake of testing by 10 percentage points (see Table 1, which is a copy of Table 2 in the Research Strategy).

As is commonly done for 2X2 factorial trials that seek to separately test for main effects of each of the two factors, our study is powered to detect the effects of the price reductions of each commodity (RDT and ACT) independent of the price of the other commodity. That is, for the purposes of our power calculations we assume no statistical interaction between the two commodities because our previous evidence suggests that any interaction effects between the prices in the two commodities are likely to be small and therefore not large enough in terms of public health importance to choose to power on such interactions [1]. That is, while we expect the uptake of testing to be sensitive to the price of both the RDT and the ACT, we do not expect that price changes in one commodity will have a different effect on testing uptake depending on the price of the other commodity.

ACT Price to client if he/she tests positive for malaria (Price for RDT negative or untested client = \$1.20)	RDT Price to client		Overall Proportion Tested*
	I. \$0.20 USD (50% subsidy)	II. \$0.40 USD (No Subsidy)	
I. \$0 USD (100% subsidy)	85%	70%	77.5%
II. \$0.10-0.40 USD (67% subsidy)	75%	60%	67.5%
Overall Proportion Tested*	80%	65%	

\* Assuming the same sample size in each of the 4 study arms

**Table 1:** Aim 1 2x2 factorial study design showing the four arms and the assumed level of testing in each arm. The 67% ACT subsidy-level was chosen to match the original AMFm prices in Kenya. We do not test the non-subsidized ACT price because our aim is to identify an ACT discount level that can incentivize individuals to get tested for malaria. Input from policy-makers suggests that fully-subsidized, free RDTs may not be acceptable from a programmatic standpoint ([name], *pers. comm.*). Therefore, we do not include a 100% RDT-subsidy level.

\* Assuming the same sample size in each of the 4 study arms

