\*\* At current market prices, this subsidy level gives the following prices to the consumer: 6 tablets@\$0.10; 12 tablets@\$0.15; 18 tablets@\$0.20; 24 tablets@\$0.40.

Using a standard approach based on a two-sample Z-test for a comparison of proportions for each of the two main effects at a two-tailed 5% Type 1 error rate (alpha), our sample size should provide 90% power to detect each of our two comparisons of interest (i.e. two main effects). To determine the overall sample size of the study, we calculated the sample size needed for each of the two main comparisons of interest, and chose the larger overall sample required (see Table 2). Specifically, because we estimated that we needed a total sample size of 838 participants (i.e. of 418 participants at each of the two conditional ACT price levels) to test for the main effect of the conditional ACT subsidy price levels compared to a total sample size of 374 (i.e. of 187 at each of the two RDT price levels) to test for the main effect of the RDT price levels, we therefore needed to plan the study by using the more restrictive sample size in order to be able to address both study goals. Given that the trial will be conducted within 10 drug retail outlets, there could be clustering of outcomes due to some participants being enrolled from the same shops. Based on our ongoing work in the region, we expect such clustering to be minimal with an intra-class correlation coefficient of at most 0.008. Even with this level of clustering, we would still have at least 80% power to detect our expected effect sizes.

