Although a priori we do not anticipate a significant interaction effect, we will perform an additional test to evaluate that assumption. If, as expected, a significant interaction effect is not detected, we will perform our planned tests of the main effects of each of the factors (see the first column in Table 2). Thus, we will have conducted three total significance tests, and will adjust for familywise Type 1 error rate using the Bonferroni correction ( $\alpha=0.05/3=0.0167$ ). As shown in the last column of Table 2, we would still have 80% power to detect the expected effect sizes with the total sample size of 838, given that Bonferroni correction is a conservative method of familywise error rate adjustment. We will use different error rate allocation methods to gain more power in statistical analysis. In the unlikely case that a significant interaction effect exists, we will instead test the conditional effects of each of factor and adjust for Type I error accordingly (as described in section 4.2; see Table 3).

**Table 2:** Expected effect sizes for the main comparisons of interest and sample size required for 80%,

Description of Comparison	Expected Increase in Testing Uptake	Total sample size required for 90% power ( $\alpha=0.05$ )	Total sample size required for 85% power ( $\alpha=0.0167$ )	Total sample size required for 80% power ( $\alpha=0.0167$ )
Effect of reducing conditional ACT price from \$0.40 (67% subsidy) to \$0.00 (100% subsidy)	10 percentage points (from 67.5% to 77.5%)	838	936	832
Effect of reducing RDT price from \$0.40 (no subsidy) to \$0.20 (50% subsidy)	15 percentage points (from 65% to 80%)	374	414	370

85%, and 90% power to detect those effect sizes (with two-tailed Type 1 error set at 0.0167 and 0.05, and using standard methods for two-sample comparison of proportions).

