## 4 Statistical Analysis Plan

### 4.1 Demographic and Clinical Characteristics (“Table 1”)

We will use principle components analysis to define a wealth index. No significance tests will be performed to test for differences at baseline. Descriptive statistics for continuous variables will include the mean, standard deviation, median, range and the number of observations. Categorical variables will be presented as numbers and percentages.

### 4.2 Analyses Plan for Aim 1

As per the assumptions used in our sample size calculations (see section 2.4), we anticipate there will be no significant interaction effect between RCT and conditional ACT subsidy levels. However, we will evaluate this assumption to protect our analysis from an unexpected interaction effect. Since the assumption of no interaction effect was in terms of risk differences (see Table 1), the test for interaction will also be performed on the absolute scale, though the primary effect measure of interest is the relative risk ratio (RR) and the test results of interaction effect may differ on different scales. If there is no significant interaction effect as expected, we will report the average effect for each of RDT subsidy and conditional ACT subsidy on the proportion of testing uptake on the relative scale. In the unlikely case that a significant interaction effect is detected, we will report the effect of each factors conditional on the other on the relative scale (see Table 3). In either case, adjustment for familywise Type 1 error rate is necessary for multiple hypothesis tests. In our sample size justification (section 2.4) we used a conservative Bonferroni correction; however, in practice, we will use an alpha allocation strategy that splits a 5% Type 1 error rate across our tests in a manner that reflects the a priori importance of each test and provides more power to detect the expected effect sizes. As mentioned previously, the primary effect measure is on the relative scale. However, due to the nature of the model, interpretable relative risk ratios cannot be derived for the average effects. Instead, approximation of the relative risk ratios on log scale will be reported. Different coding methods will not solve this problem, but we choose to use effect coding over dummy coding because effect coding, with the orthogonality property, allows for interpretable main effects

regardless of the presence of an interaction effect. Details of the statistical analysis are as follows.

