In the primary model (Model 1),  $\beta_0$  represents the overall mean of log-mean level (i.e. log-proportion) of testing uptake across all treatment arms.  $\beta_1$  represents the deviation of the log-proportion of testing uptake from the overall mean when reducing the price of the RDT from \$0.40 to \$0.20, averaged across ACT subsidy levels, while  $\beta_2$  represents the deviation of the log-proportion of testing uptake from the overall mean when reducing the price of the ACT, conditional on a positive test, from \$0.40 to \$0, averaged across RDT subsidy levels.  $\beta_3$  represents the interaction effect between the two price changes: it is the additional effect on log-proportion of testing uptake when both commodities are offered at the lower price level or higher price level, and also the negative additional effect if only one of RDT and ACT is offered at a lower price level. Relative risk ratio for the average effect of each of the price reductions cannot be obtained due to the nature of the model. However, an approximation of it can be obtained by exponentiating the parameters and deriving corresponding 95% confidence intervals.

In the secondary model (Model 2),  $\beta_0$  represents the overall mean of the proportion of testing uptake across all treatment arms.  $\beta_1$  represents the deviation of the proportion of testing uptake from the overall mean when reducing the price of the RDT from \$0.40 to \$0.20, averaged across ACT subsidy levels, while  $\beta_2$  represents the deviation of the proportion of testing uptake from the overall mean when reducing the price of the ACT, conditional on a positive test, from \$0.40 to \$0, averaged across RDT subsidy levels.  $\beta_3$  represents the interaction effect between the two price changes: it is the additional effect on the proportion of testing uptake when both commodities are offered at the lower price level or higher price level, and also the negative additional effect if only one of RDT and ACT is offered at a lower price level. Absolute risk differences and corresponding 95% confidence intervals can be obtained by directly evaluating the model parameters.

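### SAP 4.2 wrongly says that Model 1 cannot give an average risk ratio; the standardised ratio is available from it and matches the stated hypotheses, although the numerical difference at the planning values is small

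*SAP*

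**What the plan says.** The primary hypotheses (SAP 1.2.1) concern a proportion: "RDT uptake (i.e. the proportion of clients who are tested with an RDT) will increase" when one price falls, averaged over the levels of the other price. SAP 2.4, Table 1, is described as "showing the four arms and the assumed level of testing in each arm". Its margins, 80% v 65% for the RDT price and 77.5% v 67.5% for the ACT price, are simple means of the cells, and the sample-size Z-test compares those margins.

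SAP 4.2 names the risk ratio as the primary effect measure. It fits Model 1 (log link, factors coded +1/-1, interaction retained) and bases the optimisation decision on it. It says twice that the average risk ratio is out of reach: "interpretable relative risk ratios cannot be derived for the average effects" and "Relative risk ratio for the average effect of each of the price reductions cannot be obtained due to the nature of the model". In its place the SAP offers an approximation, obtained by exponentiating the parameters. Table 3 defines contrasts 1a and 1b as 2β1 and 2β2 in Model 1, each tested at alpha 0.02.

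Protocol 7.4 says only that "we will estimate the overall ACT subsidy effect and the overall RDT subsidy effect by taking relative contrasts from the model".

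**The concern.** If the statement is wrong, the primary result would be reported as an approximation to something that the fitted model gives directly. Contrasts 1a and 1b would also test an average on the log scale, while the hypotheses, the planning table and the power calculation all use averages of proportions.

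There is a reporting hazard as well. With +1/-1 coding, one coefficient is half the log effect. The text on exponentiating the parameters omits the factor 2 that Table 3 includes, so an analyst who follows the text would report a much smaller ratio than one who follows the table.

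**Working it through.** **Inputs.** Uptake by (RDT subsidy, ACT subsidy), SAP 2.4 Table 1: (50%, 100%) 0.85; (50%, 67%) 0.75; (0%, 100%) 0.70; (0%, 67%) 0.60. There are 210 clients per arm (SAP 1). Alpha is 0.02 per main effect (SAP 4.2), taken as two-sided, so the critical value is 2.326.

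**Plan's own figures.** The pooled two-sample Z-test gives totals of 834 and 370 at 90% power and alpha 0.05, against the stated 838 and 374 (within about 1%). At alpha 0.0167 it gives 936, 832, 414 and 370, exactly as in SAP Table 2. The planning calculation is therefore a comparison of the arithmetic margins.

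**Model 1 coefficients at these values.** The log uptakes are -0.1625, -0.2877, -0.3567 and -0.5108.
- β1 = (-0.1625 - 0.2877 + 0.3567 + 0.5108)/4 = 0.1043
- β2 = (-0.1625 + 0.2877 - 0.3567 + 0.5108)/4 = 0.0698
- β3 = (-0.1625 + 0.2877 + 0.3567 - 0.5108)/4 = -0.0072

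So no interaction on the additive scale, which the SAP assumes, implies a small non-zero β3 on the log scale.

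**The average risk ratio from those coefficients.**
- RDT: exp(2β1) × cosh(β2+β3)/cosh(β2-β3) = 1.2320 × 1.00196/1.00297 = 1.2308 = 80/65
- ACT: exp(2β2) × cosh(β1+β3)/cosh(β1-β3) = 1.1499 × 1.00472/1.00623 = 1.1481 = 77.5/67.5

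Covariates enter Model 1 without arm interactions under a log link, so their factor cancels from the ratio. The standard error follows by the delta method from the covariance matrix that the SAP already specifies.

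**What the planned contrasts estimate.** exp(2β2) = √[(0.85/0.75) × (0.70/0.60)] = √(1.1333 × 1.1667) = 1.150. exp(2β1) = √[(0.85/0.70) × (0.75/0.60)] = 1.232. These are geometric means of the two conditional risk ratios. They equal the standardised ratio only in special cases, such as β3 = 0.

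**Literal reading of the text.** exp(β1) = 1.11 and exp(β2) = 1.07, against 1.23 and 1.15 from the 2β contrasts in Table 3.

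**Power, ACT factor.** Power = Φ(z - 2.326).
- Log contrast: effect 2β2 = 0.1397; variance = ¼ Σ(1-p)/(np) = 0.001911; SE 0.0437; z = 3.19; power 80.7%.
- Standardised ratio: effect ln(0.775/0.675) = 0.1382. Variance = [(0.1275+0.21)/(4×210)]/0.775² + [(0.1875+0.24)/(4×210)]/0.675² = 0.000669 + 0.001117; SE 0.0423; z = 3.27; power 82.7%.

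For the RDT factor the same steps give 99.3% and 99.4%. A 200,000-run binomial simulation gave 81.5% v 83.5% for ACT. A 1,500-run GEE simulation with ICC 0.008 gave 83.1% v 85.0%, using robust standard errors without the Kauermann-Carroll correction. With every arm at 72.5%, both tests rejected in the upper tail about 1.0% of the time, as they should.

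**Sensitivity to interaction, margins held fixed.**

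| Additive interaction | exp(2β2) | ACT power, log contrast | ACT power, standardised |
|---|---|---|---|
| -8 points | 1.157 | 84.0% | 82.9% |
| 0 | 1.150 | 80.7% | 82.7% |
| +8 points | 1.143 | 77.0% | 82.7% |

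The standardised ratio is 1.148 in all three rows. The 1% interaction test would detect an 8-point interaction only about 11% of the time.

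**The case against.** The strongest reply is that little changes. The estimates differ in the third decimal at the planning values, and within 0.01 for ACT even with an 8-point interaction. RDT power is essentially the same. The SAP discloses that its figure is an approximation, and Model 2 already supplies the average risk difference (twice its coefficient), which is the absolute form of the planning comparison. All of that stands, and it limits the weight of the point. It does not make the two statements correct.

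Several stronger readings are tempting, and the documents do not support them:
- **The planned estimate is uninterpretable.** It is the geometric mean of two conditional risk ratios, which has a clear meaning. It is simply not the average of proportions used in planning.
- **The standardised ratio always has more power.** The table above shows the order reversing at -8 points.
- **The planned test falls below 80% power.** The log contrast does give 78.9% at alpha 0.0167, but that is the Bonferroni planning level. The tests use 0.02, where the figure is 80.7%.
- **Protocol and SAP conflict.** Protocol 7.4 promises relative contrasts from the model without fixing the scale of averaging, and exp(2β) is one such contrast.

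It is also fair that neither simulation applied the small-sample correction planned for 10 outlets. They support the comparison between the two tests, not an absolute power for the trial.

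**Conclusion.** Wrong as written, with small numerical consequences. The two statements in SAP 4.2 that an average risk ratio cannot be obtained or derived are incorrect, and this is an algebraic fact that does not depend on the planning values. The standardised ratio is the relative form of the comparison in the planning margins and sample-size test, and it fits the hypotheses as worded; the planned contrasts target a different, though legitimate, average.

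At the assumed uptakes with 210 per arm, the ACT ratio is 1.148 v 1.150 and ACT power at two-sided alpha 0.02 is 82.7% v 80.7%; the RDT contrast barely moves. These power figures assume no clustering, no covariates and no missing outcomes. The largest numerical risk is the missing factor 2 in the text: 1.11 and 1.07 instead of 1.23 and 1.15.

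**What to change.** In SAP 4.2:
- Delete the two statements that the average risk ratio cannot be obtained or derived.
- Define contrasts 1a and 1b as the standardised risk ratio from Model 1: mean fitted uptake with the factor at +1 divided by mean fitted uptake with it at -1, averaged equally over the other factor and over the observed covariates. Test log(RR) = 0 with a delta-method standard error from the Kauermann-Carroll-corrected covariance matrix.
- Leave contrasts 2a to 2d as they are.
- If exp(2β) is also reported, write the factor 2 explicitly and label it a geometric-mean risk ratio.
- Align rows 1a and 1b of Table 3 and shell Table B3.

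The cost is a few lines of SAP text and one post-estimation step, with no new data. The analyst should confirm that the software passes the corrected covariance matrix to that step. If it does not, the closed form above and its gradient can be coded directly.

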In our analysis, we will fit a modified Poisson regression model with log link to estimate risk ratios as the primary effect measure (i.e. an effect measure on the relative scale, see Model 1) [2, 3]. Such an approach assumes a Poisson distribution for the binary outcome and then 'fixes' the estimated standard errors to correct for model misspecification (i.e. using a Poisson rather than binomial model). It is the preferred modelling approach to estimate RRs as it avoids some of the convergence issues that may be encountered when using the alternative log-binomial regression approach whilst maintaining good statistical properties. In addition, we will fit a modified Poisson regression model with identity link to estimate risk differences as the secondary effect measure (see Model 2), since the assumption of no interaction effect is made on the absolute scale. However, the optimization decision will be based the primary model (i.e. on the relative scale). All analyses will be based on the intention-to-treat principle whereby all clients will be included in the analysis irrespective of whether they complied with the intervention.

The models will have the following form:

$$\text{Model 1: } \log(E(Y_{ij})) = \beta_0 + \beta_1 \text{RDT\_SUBSIDY\_50\%}_{ij} + \beta_2 \text{ACT\_SUBSIDY\_100\%}_{ij} + \beta_3 \text{RDT\_SUBSIDY\_50\%}_{ij} * \text{ACT\_SUBSIDY\_100\%}_{ij} + \mathbf{w}_{ij} \boldsymbol{\alpha}$$

$$\text{Model 2: } E(Y_{ij}) = \beta_0 + \beta_1 \text{RDT\_SUBSIDY\_50\%}_{ij} + \beta_2 \text{ACT\_SUBSIDY\_100\%}_{ij} + \beta_3 \text{RDT\_SUBSIDY\_50\%}_{ij} * \text{ACT\_SUBSIDY\_100\%}_{ij} + \mathbf{w}_{ij} \boldsymbol{\alpha}$$

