where  $Y_{ij}$  is an indicator of whether client  $j$  in outlet  $i$  ( $j=1, \dots, 84$ ;  $i = 1, \dots, 10$ ), chose to get tested for malaria in the retail outlet ( $=1$  if tested,  $0$  otherwise) and  $E(Y_{ij})$  is its expected value.  $\text{RDT\_SUBSIDY\_50\%}_{ij}$  is an indicator for whether the client received the lower RDT price of \$0.20 ( $=1$  if they received the offer of an RDT at \$0.20,  $=-1$  if they received the offer of an RDT at \$0.40) and  $\text{ACT\_SUBSIDY\_100\%}_{ij}$  is an indicator for whether the client received the higher ACT subsidy ( $=1$  if ACT price conditional on a positive test is \$0,  $=-1$  if ACT price conditional on positive test is \$0.40). Therefore,  $\text{RDT\_SUBSIDY\_50\%}_{ij} * \text{ACT\_SUBSIDY\_100\%}_{ij}$  represents an interaction term for clients who receive both the higher RDT and ACT subsidies or both the lower RDT and ACT subsidies ( $=1$  in two situations: a. RDT is offered at \$0.20 and ACT is offered at \$0 conditional on a positive test or b. RDT is offered at \$0.40 and ACT price conditional on positive test is \$0.40,  $=-1$  otherwise).  $\mathbf{w}_{ij}$  is a vector of potential confounder variables (e.g., age, gender, wealth, education) to account for possible imbalances between study arms. To account for possible clustering due to multiple individuals being randomized within 10 different (randomly-sampled) outlets we will use a generalized estimating equations (GEE) approach with

exchangeable working covariance matrix, robust standard errors (to correct for model misspecification due to specifying a Poisson distribution) and finite-sample correction (to obtain unbiased standard errors estimates using the Kauermann-Carroll method)[4, 5]. Regression diagnostics, including residual plots, will be used to verify model assumptions. Because all secondary outcomes are binary, we will use the same modelling approach to compare these outcomes.

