Our two primary goals are to determine whether RDT uptake increases significantly when the price of the RDT is reduced from \$0.40 (no subsidy) to \$0.20 (a 50% subsidy), averaged over the ACT price levels (i.e. the main effect), and when the price of the ACT conditional on a positive test is reduced from \$0.40 to \$0 (67% subsidy vs 100% subsidy), averaged over the RDT price levels (i.e. the main effect). That is, we wish to test for the main effects of these two commodities. These can be evaluated by testing the null hypotheses  $H_0: 2\beta_1=0$  and  $H_0: 2\beta_2=0$ , with 2% Type 1 error rate respectively. Although, a priori, we hypothesized no statistical interaction

on absolute scale in our sample size calculations, a secondary aim is to determine whether the effect of each of the price changes depends on the price of the other commodity. This can be tested by evaluating the null hypothesis  $H_0: \beta_3=0$  in model 2 on the absolute scale with 1% Type 1 error rate. If this effect is statistically different from zero, we will report the effect of the price reductions of each commodity conditional on the price of the other commodity, with a Type 1 error rate of 1% respectively. If, however, as we expect, there is no statistically significant or scientifically meaningful interaction (i.e.  $\beta_3$  is close to zero), we will estimate the average effects from a model with interaction to match the study design with a Type 1 error rate of 2% respectively. The allocation of Type 1 error rate is based on the a priori importance of the hypothesis tests and provides more power than the conservative strategy employed in our sample size calculations (section 2.4). Contrasts of interest are summarized in Table 3.

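### The two sentences in SAP section 4.2 on obtaining risk ratios and risk differences omit the factor 2 that +1/−1 coding requires; only reported magnitudes are at risk

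*SAP*

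**What the plan says.** SAP section 4.2 opts for effect coding: "we choose to use effect coding over dummy coding because effect coding, with the orthogonality property, allows for interpretable main effects". The model definitions then set each price factor to +1 for the higher subsidy and −1 for the lower one.

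The SAP goes on to interpret the coefficients. Under Model 2 (identity link), β1 "represents the deviation of the proportion of testing uptake from the overall mean when reducing the price of the RDT from" the higher to the lower RDT price. The extraction rules follow:

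- Model 1 (log link), average risk ratio: "an approximation of it can be obtained by exponentiating the parameters and deriving corresponding 95% confidence intervals".
- Model 2, risk difference: "Absolute risk differences and corresponding 95% confidence intervals can be obtained by directly evaluating the model parameters".

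The same section states the main-effect null hypotheses on 2β1 and 2β2 without naming a model. SAP Table 3 lists 2β1, 2β2 and the four conditional contrasts, all doubled and all assigned to Model 1. Its only Model 2 row is the interaction, 2β3. Section 4.2 makes the risk difference the secondary effect measure ("we will fit a modified Poisson regression model with identity link to estimate risk differences as the secondary effect measure"), and section 5.5 also promises to present it. Protocol section 7.4 plans risk differences as well but gives no coefficient contrast.

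**The concern.** With +1/−1 coding the two price levels lie two units apart. A coefficient is therefore the distance from the grand mean to one level, which is half the distance between the levels. The SAP recognises this in its hypotheses and in Table 3, but not in the two sentences that say how reported estimates are obtained.

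If an analyst followed those sentences to the letter, each average risk difference would be halved and each average risk ratio would be replaced by its square root. The interval shrinks with the estimate and the p-value does not move, so no test would flag the slip. The risk difference is offered as the intuitive measure of public health impact, so its size matters to readers. Section 4.2 also applies the same modelling approach to the secondary outcomes, so the wording carries over to them.

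**Working it through.** **Inputs.**
- Assumed uptake from SAP Table 1 (repeated in Table C2): 85% with both higher subsidies; 75% with the 50% RDT and 67% ACT subsidies; 70% with no RDT subsidy and the 100% ACT subsidy; 60% with no RDT subsidy and the 67% ACT subsidy.
- 210 per arm, from SAP section 1.
- Models 1 and 2 with +1/−1 coding and the interaction, from SAP section 4.2.
- Simplifications made here: independent outcomes, no covariates, limits at ±1.96 standard errors.

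**1. The plan's own figures.** RDT: (85 + 75)/2 − (70 + 60)/2 = 80 − 65 = 15 points. ACT: (85 + 70)/2 − (75 + 60)/2 = 77.5 − 67.5 = 10 points. Both match SAP Table 2.

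**2. Model 2 coefficients.** Mean uptake is β0 + β1 at the lower RDT price and β0 − β1 at the higher one, so the difference is 2β1.
- β1 = (0.85 + 0.75 − 0.70 − 0.60)/4 = 0.075
- β2 = (0.85 − 0.75 + 0.70 − 0.60)/4 = 0.050
- β3 = (0.85 − 0.75 − 0.70 + 0.60)/4 = 0

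Only 2β1 = 0.15 and 2β2 = 0.10 return the planned 15 and 10 points.

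**3. Intervals.** Σp(1 − p) = 0.1275 + 0.1875 + 0.2100 + 0.2400 = 0.765. SE(β) = √(0.765/210)/4 = 0.01509, and SE(2β) = 0.03018.

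| Average risk difference | Parameter taken as it stands | Doubled contrast |
|---|---|---|
| RDT price | 7.5 points (95% CI 4.5 to 10.5) | 15.0 points (9.1 to 20.9) |
| ACT price | 5.0 points (95% CI 2.0 to 8.0) | 10.0 points (4.1 to 15.9) |

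Neither undoubled interval contains the difference that it would be reported for.

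**4. Tests.** z = 0.075/0.01509 = 0.150/0.03018 = 4.97 for the RDT, and 0.050/0.01509 = 0.100/0.03018 = 3.31 for the ACT. Doubling leaves z and p unchanged.

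**5. Model 1.** β1 = (ln 0.85 + ln 0.75 − ln 0.70 − ln 0.60)/4 = 0.1043; in the same way β2 = 0.0698 and β3 = −0.0072.
- exp(β1) = 1.110 against exp(2β1) = 1.232; the ratio of marginal proportions is 80/65 = 1.231.
- exp(β2) = 1.072 against exp(2β2) = 1.150; the ratio of marginal proportions is 77.5/67.5 = 1.148.

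Table 3's conditional contrasts, exponentiated, return the exact cell ratios: 75/60 = 1.250, 85/70 = 1.214, 70/60 = 1.167 and 85/75 = 1.133. Table 3 is therefore correct for the risk ratio, and the sentence on exponentiating the parameters is what conflicts with it.

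**6. Is the Model 2 contrast given elsewhere?** The one Model 2 row in Table 3, 2β3, concerns the interaction and is not a price effect. Later in section 4.2 the SAP says only that risk differences come from replacing the log link with an identity link. Neither place writes 2β1 or 2β2 for Model 2.

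**The case against.** The best defence is that the Model 2 sentence concerns scale. Model 1 parameters have to be exponentiated; Model 2 parameters need no back-transformation. It does not say that the risk difference equals β1. The same paragraph calls β1 a deviation from the overall mean, the nulls on 2β1 and 2β2 carry no model label, both models share one linear predictor, and the SAP says that only the link changes. All of this points to doubling, a careful analyst would probably double, and the arm percentages in Table B2 would expose a halved figure.

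Most of this stands. A reader might infer that the SAP prescribes a halved risk difference, or that the reported results will be wrong. The documents do not support that: the wording is loose and the surrounding text leans the right way. What does not fall away is that the parallel risk-ratio sentence drops the same factor and contradicts Table 3. The Model 2 sentence is also the only place that says how the parameters become a risk difference and its interval.

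A reader might also infer that Table 3 is deficient because it lacks Model 2 rows for average and conditional risk differences. That goes too far. Table 3 lists tests and splits the 5% error rate among them (0.01 + 0.02 + 0.02 when the interaction is not significant), and the risk difference has no share of alpha. For a significant interaction, one sentence says "we will report the effect of the price reductions of each commodity conditional on the price of the other commodity" without naming a scale, but the opening of section 4.2 commits to those conditional effects on the relative scale. Conditional risk differences are not specifically promised.

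**Conclusion.** The point holds as an inconsistency within SAP section 4.2. For the risk ratio, the extraction sentence conflicts with Table 3, and Table 3 is right. For the risk difference, the contrast is implied but never written, and the sentence that comes closest omits the factor 2.

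Read literally, the text gives 7.5 and 5.0 points instead of 15 and 10, and risk ratios of 1.11 and 1.07 instead of 1.23 and 1.15. The halving of the risk difference and its limits follows from the coding alone, so it does not depend on covariates, clustering or the standard-error method. The particular values rest on the SAP's assumed rates, and the interval widths also on 210 per arm, independence and no covariates.

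It would be wrong to infer that any conclusion of the trial is threatened. The tests, p-values and interaction test are the same with or without the factor, and the SAP bases its optimization decision on the relative-scale model, where Table 3 is correct. At stake is the size of the reported estimates, above all the secondary effect measure. The correction is worth making because it costs almost nothing.

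**What to change.** Rewrite the two extraction sentences in SAP section 4.2 to state:

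- The approximate average risk ratio is exp(2β1) for the RDT price and exp(2β2) for the ACT price, from Model 1. Keep the qualifier that this is an approximation.
- The average risk difference is 2β1 and 2β2, from Model 2.
- Confidence limits are computed for the doubled contrasts.
- If conditional risk differences are also reported, they are 2β1 − 2β3 and 2β1 + 2β3 for the RDT price, and 2β2 − 2β3 and 2β2 + 2β3 for the ACT price, from Model 2.

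Leave Table 3 unchanged as the list of tests with its alpha split, and add no tests. The cost is a few lines of text, with no change to design, data collection, sample size or hypothesis tests.
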